7.2.2. Per Protocol Set

The Per Protocol Set will include all participants in the Full Analysis Set without any major protocol deviations that could affect efficacy. The review of major protocol deviations will be completed and the decision on whether the deviation affects efficacy and results in removal of a participant from the Per Protocol Set will be documented before database unblinding. The Per Protocol Set will exclude full analysis set participants satisfying any of the following conditions:

- Study Drug Adherence (defined in Section 8.2.7) < 75%
- Inappropriate drug consumption (typically due to incorrect kit dispensation): if the participant consumed at any time during the study any study drug that the participant is not randomized to
- Day 91 efficacy assessment done 3 days or more after the last dose
- Essential tremor duration of less than 3 years
- Prohibited essential tremor medication during the treatment phase of the study (after completing the treatment is fine)
- Any other major protocol deviations that the protocol deviation review committee (PDRC) documents as impacting the primary efficacy analysis prior to the database lock.

7.3. Safety Analysis Set

The Safety Analysis Set is defined as all participants administered IP. The Safety Analysis Set will be used for safety analysis.

8. STATISTICAL ANALYSIS

8.1. General Considerations

All participant data, including those that are derived, that support the tables and figures will be presented in the participant data listings. Some data may be presented only in participant data listings, some may be presented with a corresponding table or figure; these will be indicated in relevant sections below. All summaries will be provided by treatment group.

For all safety and efficacy analyses where applicable, baseline is defined as the last nonmissing measurement prior to the first dose of IP. A baseline composite endpoint will be calculated based on baseline individual endpoints.

Continuous endpoints will be summarized with n, mean, standard deviation (SD), median, first and third quartiles (Q1, Q3), minimum (min), and maximum (max). The minimum and maximum will be reported with the same number of decimal places as the source (raw) data. In general, mean and median will be reported to 1 decimal place more than the source (raw) data and standard deviation will be reported to 2 decimal places more than the source (raw) data; source data reported to several decimal places will be reported to an appropriate number of decimals places as determined by the study team. Any values that require transformation to standard units (metric or SI) will be converted with the appropriate corresponding precision. In addition, change from baseline values will be calculated at each time point and summarized descriptively.

Categorical variables will be summarized using counts and percentages. Percentages will be presented to 1 decimal place unless otherwise specified.

Participants will be summarized according to randomized treatment for all analyses except for safety analyses. For safety analyses, participants will be summarized according to treatment received.

P-values will be reported to four decimal places, with p-values less than 0.0001 reported as "<0.0001". P-values larger than 0.9999 will be reported as ">0.9999".

8.2. Background Characteristics

8.2.1. Participant Disposition

The summaries of disposition will include number of participants who were screened (All Participants Set), who were randomized, who received study drug, the number and percentage of participants who completed the study and who prematurely withdrew from the study, primary reasons for not completing the study, who completed treatment, who discontinued treatment prematurely, and primary reasons for discontinuing treatment.

Study completion summary and treatment completion summary will be based on participants who received study drug (Safety Analysis Set). Percentages will be calculated based on the participants randomized and dosed. These data will be provided by randomized treatment groups, by stratum (monotherapy cohort and adjunct therapy cohort) and overall.

If a participant is rescreened because he/she has been a screen failure the first time, the status of the participant will be determined from the second screening. In the count of screened participants, this participant will be counted only once.

The number of participants in each of the analysis sets will also be summarized and presented by treatment arm, by stratum (monotherapy cohort and adjunct therapy cohort) and overall. Randomization data (date and time of randomization, randomization number, and randomized treatment) and participants excluded from each analysis set will be listed but not summarized.

A completer for the study is defined as one who completed all study phases, including the final follow-up visit (Day 104 visit) and is derived from the Study Disposition CRF page with completion question answered Yes. A participant is defined as prematurely discontinuing treatment if treatment ends before the final dose of study drug taken on Day 90, and is derived from the Study Treatment Completion/Discontinuation CRF page with completion question answered No. The primary reason for study discontinuation or treatment discontinuation of a participant is provided in the respective CRF page.

8.2.2. Protocol Deviations

Protocol deviations will be captured on the eCRF and categorized by the study team as major and minor deviations without any unblinding information. The major deviations will be summarized by type and by randomized treatment using the Full Analysis Set. The minor deviations will be included in the listing. The COVID-19 related protocol deviations will also be summarized. Summarization will be done by stratum (monotherapy cohort and adjunct therapy cohort) and overall.

Inclusion/exclusion violations will be listed but not summarized.

8.2.3. Demographics and Baseline Characteristics

Demographic data (age, sex, race, and ethnicity) and baseline characteristics (height, weight, BMI, dominant upper limb) will be summarized with descriptive statistics by treatment group using the Safety Analysis Set. This summarization will be done by stratum (monotherapy cohort and adjunct therapy cohort) and overall.

Baseline subgroups will be summarized for the following categories:

- Race (Black or African American, White, Asian, Other)
- Sex (Female, Male)
- Age (<65, 65 to 80 years)
- BMI (<18.5, 18.5 to <25, 25 to <30, ≥30 kg/m²)

Listings will be provided for demographics, other baseline characteristics, and informed consent data.

8.2.4. Medical/Surgical History

Summarization of medical and surgical history data will be done by stratum (monotherapy cohort and adjunct therapy cohort) and overall.

Medical/surgical history will be coded to Medical Dictionary for Regulatory Activities (MedDRA) terms, using Version 24.1, or higher. The MedDRA version will be included in the footnotes of related outputs. Medical/surgical history will be summarized using discrete summary statistics for each MedDRA System Organ Class (SOC) and Preferred Term (PT) by treatment group for the Safety Analysis Set.

Medical history related to ET including age at diagnosis, age at onset of ET, tremor responsiveness to alcohol, past treatments for ET, response to therapy, and reason for discontinuation will be listed. Age at diagnosis, age at onset of ET, past treatment for ET (yes/no), and whether alcohol helps participant tremor will also be summarized.

The disease subgroups will be summarized for the following categories:

- Age at ET diagnosis (<40 years, 40 to 60 years, >60 years)
- Age participant thinks ET started (<20 years, 20 to <40 years, 40 to 60 years, >60 years)
- Years with ET diagnosis (<3 years, 3 to <6 years, 6 to 10 years, >10 years)
- Years since participant thinks ET started (<3 years, 3 to <6 years, 6 to 10 years, >10 years)
- Alcohol helps tremor: Yes (Intermediate, Worked Well), No (No, a little), NA
- Past treatment for ET (Yes, No)
- Response to past treatment for ET: Yes (Intermediate, Worked Well), No (No, a little), NA
- Reason for discontinuation of past treatment for ET (drug interactions, lack of efficacy, physician decision, side effects, other)

8.2.5. Prior and Concomitant Medications

Medications will be recorded at each study visit and coded into drug class (anatomical therapeutic chemical [ATC] Level 2) and PT using World Health Organization-Drug dictionary (WHO-DD) Global B3 September 2021, or later.

All medications taken within 30 days prior to signing the informed consent through the duration of the study (including start and end dates, route, dose/units, frequency, and indication) will be recorded on the electronic case report form (eCRF); all psychotropic medications taken in the 30 days prior to screening and all medications taken at any time prior to signing the informed consent through the duration of the study for ET will also be recorded.

Those medications taken prior and having use ending prior to the initiation of the start of IP will be denoted "Prior". Those medications taken prior to the initiation of the IP and

continuing beyond the initiation of the IP, or those medications started at the same time or after the initiation of the IP will be denoted "Concomitant".

Medications will be flagged in the listing according to whether they are "Prior" or "Concomitant" as defined above. In the event of a missing start or stop date associated with a medication, only the classification (prior and/or concomitant) will be imputed using the algorithm described in Appendix B. Dates will not be imputed.

Prior and concomitant medications will be summarized separately for the Safety Analysis Set as the number and percentage of participants with each medication at both the ATC and PT levels; these summarizations will be done by stratum (monotherapy cohort and adjunct therapy cohort) and overall. Details of prior and concomitant medications will be listed by participant, start date, and verbatim term.

8.2.6. Investigational Product Exposure

Total drug exposure (in mg) is defined as the total IP in mg for SAGE-324 that was taken during the study. Total drug exposure for participants randomized to placebo is zero unless the participant has taken SAGE-324 by mistake, in which case the total drug exposure comes from SAGE-324 exposure. If a participant skips a dose on any of the days, the dose taken is 0 mg.

Total exposure duration to IP (in days) is defined as (date of last dose – date of first dose + 1). Note that this does not exclude days when the dose has been missed.

For participants that have been dispensed with SAGE-324 15mg, 30mg, and 45mg prepacked kit, but do not take the full 4 tablets, from a safety perspective, the general rule is that the tablets taken are assumed to be the active tablet(s) in the dispensed kit before counting any placebo tablets. For example, for a 15mg pre-packed kit, if the patient takes only one tablet, the tablet would be the 15mg tablet. If the patient takes 2 tablets, it would be assumed that they took the one 15mg tablet and one placebo tablet.

Planned exposure for the participants who complete the treatment period is defined as follows:

- 1. For participants randomized to the SAGE-324 15 mg group, 90 days of treatment times 15 mg
- 2. For participants randomized to the SAGE-324 30 mg group, 90 days of treatment times 30 mg
- 3. For participants randomized to the SAGE-324 60 mg group, the sum of 14 days of treatment times 15 mg, 14 days of treatment times 30 mg, 14 days of treatment times 45 mg, and 48 days of treatment times 60 mg

Planned exposure for the participants who discontinue the treatment period early is defined as follows:

1. For participants randomized to the SAGE-324 15 mg group, total exposure duration times 15 mg

Statistical Analysis Plan Methods Version 1.0 17-Jun-2024 Protocol Number: 324-ETD-202 (Version 6.0 2 November 2023)

- 2. For participants randomized to the SAGE-324 30 mg group, total exposure duration times 30 mg
- 3. For participants randomized to the SAGE-324 60 mg treatment group
 - If 1 ≤ total exposure duration ≤ 14, then planned exposure = total exposure duration times 15 mg
 - If 15 ≤ total exposure duration ≤ 28, then planned exposure = 14 days times 15 mg + (total exposure duration 14) times 30 mg
 - If 29≤ total exposure duration ≤ 42, then planned exposure = 14 days times 15 mg + 14 days times 30 mg + (total exposure duration 28) times 45 mg
 - If 43 ≤ total exposure duration ≤ 90, then planned exposure = 14 days times 15 mg + 14 days times 30 mg + 14 days times 45 mg + (total exposure duration -42) times 60 mg

For participants randomized to placebo, planned exposure is not applicable.

Percent of the planned exposure received is defined as the total drug exposure, divided by planned exposure, times 100.

Total drug exposure, total exposure duration, and percent of planned exposure received will be summarized using the Safety Analysis Set by randomized treatment group. Also, the number and percentage of participants with percent of planned exposure <80%, 80% to <100%, and \geq 100% will be summarized. Summarization will be provided by stratum (monotherapy cohort and adjunct therapy cohort) and overall.

8.2.7. Investigational Product Adherence

IP adherence (%) is defined as the number of tablets taken, divided by the number of tablets planned to be taken, times 100.

The schedule of IP administration is that all participants will take 4 tablets per day in a mix of active and placebo tablets to achieve a dose of 15 mg (1 SAGE-324 tablet and 3 placebo tablets per dose), 30 mg (2 SAGE-324 tablets and 2 placebo tablets per dose) or 60 mg (4 SAGE-324 tablets). The number of tablets planned to be taken is defined as 4 times 90 for the participants who complete the treatment period. For participants who discontinue treatment early, the number of tablets planned to be taken is defined as 4 times total exposure duration (see Section 8.2.6).

IP adherence will be summarized using Safety Analysis Set and randomized treatment group. Number and percentage of participants with IP adherence in categories <75%, 75 to 100%, >100% will be provided. Summarization will be provided by stratum (monotherapy cohort and adjunct therapy cohort) and overall.

8.3. Efficacy Analysis

8.3.1. **Definition of Efficacy Variable(s)**

8.3.1.1. Primary Efficacy Assessment

For the TETRAS Performance Subscale Item 4 (upper limb), three maneuvers/assessments will be completed for both arms, first for the right arm and then for the left, specifically Item 4a, limbs extended forward maneuver (postural tremor), Item 4b, wing-beating [elbows flexed] maneuver (postural tremor), and Item 4c finger-nose-finger maneuver (kinetic tremor). Each assessment is rated on a 0 to 4 scale of severity in 0.5-point increments, with higher scores indicating more severe tremor. The Performance Subscale Item 4 (upper limb) total score range for a given side (left or right) is 0 to 12, and for both sides combined is 0 to 24; if any component of a total score for a side or both sides is missing, the total score is not computed. Assessment of the TETRAS Performance Subscale Item 4 (upper limb) occurs at Screening and Days 1, 8, 15, 29, 43, 57, 71, 91/EOT, and 97.

The primary efficacy endpoint is the change from baseline in TETRAS Performance Subscale Item 4 (upper limb) total score at Day 91 in the monotherapy cohort for the Full Analysis Set.

8.3.1.2. Secondary Efficacy Assessment

The TETRAS ADL Subscale assesses how ET affects typical activities of daily living (ie, speech, eating, drinking, dressing, personal hygiene, writing, occupational impairment, social impact, and activities affected by upper limb tremor). It consists of 12 items that are each rated on a scale from 0 (normal activity) to 4 (severe abnormality), and the overall ADL score range is 0 to 48; if any component of overall ADL score is missing, the overall ADL score is not computed. Responses of 0 and 1 in TETRAS ADL Subscale Items 1 to 11 will be collapsed and analyzed as a single response of 0 = normal/slightly abnormal such that the scale becomes:

- 0 = Normal/slightly abnormal
- 1 = Mildly abnormal
- 2 = Moderately abnormal
- 3 = Severely abnormal

TETRAS Performance Subscale Item 6 (Archimedes Spiral) is assessed for both the right and left sides. Each assessment is rated on a 0 to 4 scale of severity, with higher scores indicating more severe tremor. Since Item 6 may be assessed on a scale with 0.5 point increments, the responses of Item 6 will be rescaled as:

0 = Normal/slightly abnormal (original score of 0, 0.5, 1)

1 = Mildly abnormal (original score of 1.5, 2)

2 = Moderately abnormal (original score of 2.5, 3)

Statistical Analysis Plan Methods Version 1.0 17-Jun-2024 Protocol Number: 324-ETD-202 (Version 6.0 2 November 2023)

3 = Severely abnormal (original score of 3.5, 4)

Assessment of the TETRAS ADL and Performance Subscales occurs at Screening and Days 1, 8, 15, 29, 43, 57, 71, 91, and 97.

The TETRAS ADL composite endpoint comprises Items 1 to 11 of the TETRAS ADL Subscale and Item 6 (both sides) of the TETRAS Performance Subscale, and can range in value from 0 to 39; if any component of the TETRAS ADL composite endpoint is missing, the TETRAS ADL composite endpoint is not computed.

The secondary efficacy endpoint is the change from baseline in the TETRAS ADL composite score at Day 91 in the monotherapy cohort for the Full Analysis Set.

8.3.2. Visit Windows for Efficacy Analyses

The scheduled visits will not be windowed and will be used at nominal visit value for treatment and follow-up period visits (Day 1, Day 8, Day 15, Day 29, Day 43, Day 57, Day 71, Day 91, Day 97, Day 104). Unscheduled, end-of-treatment (EOT), and early termination visits (ETV) that happen on or before one day after the last dose will be mapped to a scheduled visit for analysis using the date of collection/assessment and Day 1, first dose date, as a basis to determine study day and then study day will be mapped to the intended visit according to the visit windows specified in the Table 2. Unscheduled, EOT, or ET visits that happen on or after 1 day after the last dose will be windowed using relative days since last dose date; the mapping will follow the visit window in Table 2. To accommodate as much data as possible into analysis, these windows have been widened relative to protocol-specified operational windows to have no gap between them; these windows are used for analysis purposes only.

Scheduled Visit	Study Day of Expected Visit	Study Day Window for Visit
Screening	Day -1	Days -28 to Day -1
Day 1 Predose	Day 1 Predose	Day 1 Predose
Day 8 (±1 day)	8	Day 1 Postdose to Day 11
Day 15 (±1 day)	15	Days 12 to 22
Day 29 (±1 day)	29	Days 23 to 36

Table 2:	Visit	Windows	for	Efficacy	Analy	vsis
				•		

Scheduled Visit	Study Day of Expected Visit	Study Day Window for Visit
Day 43 (±1 day)	43	Days 37 to 50
Day 57 (±3 days)	57	Days 51 to 64
Day 71 (±3 days)	71	Days 65 to 81
Day 91 (+1 day)	91	Days 82 to 96
Day 97/last dose +7 days (±3 days) 97/last dose+ 7 days		Days 97 to 100 (last dose+6 days, last dose + 10 days)
Day 104/last dose + 14 days $(\pm 3 \text{ days})(*)$	104/last dose + 14 days	≥ Day 101 (last dose + 11 days, last dose + 17 days)

Note: Parenthesized study days and study day windows are for unscheduled, EOT, and ET visits. For participants who have discontinued treatment prematurely with either unscheduled, EOT, or ET visits on or after 6 days of the last dose, those visits should be mapped to Day 97 or Day 104 using the parenthesized visit windows listed (ie, visit date – last dose date >1).

Note: (*) The scheduled visit of Day 104/last dose visit is for efficacy analysis excluding TETRAS.

Once analysis visits are assigned based on the visit windows, all visits, including scheduled visits, unscheduled visits, and EOT/ETV visits, will be eligible for being flagged as the "analyzed record" within the analysis visit window; a participant's individual analysis visit window could potentially contain more than 1 visit. In the event of multiple visits falling within an analysis window or in case of a tie relative to number of days from the scheduled study day, the following rules will be used in sequence to determine the "analyzed record" for the analysis visit window:

- If data from the scheduled visit is available within treatment period, then the scheduled visit data will be used.
- If no data from the scheduled visit within treatment period is available, then the windowed visit data will be used.
- If more than one visit is in the same target day window, the data closest to the target day will be used.
 - If there is a tie with distance from visits to target day, the visit after the the target day will be used.

The summary by visit will use the "analyzed records" only – at most one per participant per visit. The data not flagged as the "analyzed record" will be included in listings. An unscheduled visit that does not fall under any analysis window (e.g. in case one is available after Day 107) will remain in the database and will be included in the listings.

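### SAP 8.3.2 sets conflicting cut-offs for visits after the last dose; read literally, an early stopper's unscheduled or EOT TETRAS score taken 2–5 days after the last dose has no analysis window

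*SAP*

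**What the plan says.** SAP 8.3.2 uses scheduled visits at their nominal label. Unscheduled, EOT and early-termination visits follow two other rules:

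- Visits "that happen on or before one day after the last dose will be mapped to a scheduled visit for analysis" are placed by study day.
- For later ones, "visits that happen on or after 1 day after the last dose will be windowed using relative days since last dose date", following Table 2.

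Table 2 has two relative windows. The Day 97 row reads "Days 97 to 100 (last dose+6 days, last dose + 10 days" and the Day 104 row covers last dose +11 to +17. A footnote takes TETRAS out of the Day 104 row.

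The note under Table 2 covers participants who stop early. Its first half deals with their unscheduled and EOT visits "or ET visits on or after 6 days of the last dose, those visits should be mapped to Day 97 or Day 104". Its closing words then restate the condition in a different form: "using the parenthesized visit windows listed (ie, visit date – last dose date >1". The same section says that "these windows have been widened relative to protocol-specified operational windows to have no gap between them".

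On visits outside every window, the sentence begins: "An unscheduled visit that does not fall under any analysis window (e.g. in case one is available after Day 107) will remain"; such a record is kept on file and shown only in listings. Where a window holds several records, the first rule is: "If data from the scheduled visit is available within treatment period, then the scheduled visit data will be used".

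The estimand (SAP 4.1.3 and 8.3.3.1) uses all observed on-study data through the Table 2 mapping, regardless of premature discontinuation. The MMRM takes all postbaseline clinic visits. Protocol 8.4.1 encourages anyone who stops study drug to complete an EOT visit but states no interval from the last dose. SAP 8.3.1.1 lists Item 4 at Day 91/EOT.

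**The concern.** The two mapping rules meet at one day after the last dose, but the relative rule has nothing to map to until day six. A score in between is observed, belongs to a randomized participant and is wanted by the estimand, yet it has no analysis visit. The MMRM in SAP Appendix C is indexed by analysis visit, so a score without one cannot enter.

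Handling would also be uneven. A score 0–1 days after the last dose is used at its study-day visit, one at 2–5 days is not used, and one at 6–10 days is used as Day 97. Two programmers could build different primary datasets from the same text.

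The situation is foreseeable: drug is taken at home at bedtime, so a participant can stop between clinic visits. If the last dose was late in the treatment period, the score at issue could be that participant's Day 91 value. A participant whose only postbaseline score falls in the gap would meet the Full Analysis Set definition yet add no record to the model. By-visit safety summaries use the same rules (SAP 8.4), and the notes to Tables 6 and 7 repeat the conflicting cut-off.

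**Working it through.** **Step 1: coverage by lag.** Let lag r = visit date − last dose date. Inputs are the two rules, Table 2 and its notes (SAP 8.3.2).

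| Lag r (days) | Rule that applies | Window for TETRAS |
|---|---|---|
| 0 | study day | yes |
| 1 | both rules; only the study-day rule offers a window | yes |
| 2, 3, 4, 5 | relative | none |
| 6–10 | relative | Day 97 |
| 11–17 | relative | Day 104, TETRAS excluded |
| 18 or more | relative | none |

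The study-day windows themselves are continuous from Day 1 postdose onward. The 2–5 day gap arises only where the two rules join.

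**Step 2: does the note close the gap?** It starts relative mapping at 6 days, then restates the condition as more than 1 day. The first version leaves lags 2–5 without a window. The second sends them to relative windows whose lower bound in Table 2 is still +6. Reading it as sending lags 2–5 to Day 97 overrides both the Day 97 row and the first half of the note.

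**Step 3: where would these visits fall by study day?** Let L = last-dose day of an early stopper (1–89) and visit day v = L + r with r = 2–5. There are 89 × 4 = 356 pairs.

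- By window: Day 8, 30; Day 15, 44; Day 29, 56; Day 43, 56; Day 57, 56; Day 71, 68; Day 91, 46. The sum is 356.
- Day 91 needs 82 ≤ L + r ≤ 96 with L ≤ 89, so L runs from 82 − r to 89, which is 8 + r values: 10 + 11 + 12 + 13 = 46 (13%), from last doses on Days 77–89.
- Pairs in a window whose target day was on or before the last dose: Day 8, 3; Days 15, 29, 43 and 57, 18 each; Day 71, 30. The total is 3 + 72 + 30 = 105 (29%). An attended scheduled visit would be used there anyway.
- The rest: 356 − 46 − 105 = 205 (58%), in Day 8–71 windows whose target day comes after the last dose.

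**Step 4: which pairs could be recorded as a scheduled visit?** The protocol's Schedule of Assessments permits ±1 day at Days 8, 15, 29 and 43, ±3 at Days 57 and 71, and +1 at Day 91.

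- Four visits × 3 days × 4 lags = 48.
- Two visits × 7 days × 4 lags = 56.
- Day 91 gives 4 pairs and Day 92 gives 3 (L cannot exceed 89), so 7.
- Total 48 + 56 + 7 = 111 (31%): 7 of the 46, 98 of the 205 and 6 of the 105.

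The other 356 − 111 = 245 pairs (69%) cannot be scheduled visits held in window. Of the 46 Day 91 pairs, 46 − 7 = 39 remain: 36 on Days 82–90 and 3 on Days 93–94.

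These are counts of day combinations, each given equal weight. They are not shares of participants.

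**The case against.** **The more-than-1-day reading may be the intended one.** Taken with the no-gap sentence, it suggests that every visit more than one day off drug belongs to follow-up and that the +6 bound is the slip. The score would then stay in the MMRM as Day 97. This is a fair reading and nothing in the SAP rules it out. It shows that exclusion is not the only possible outcome, but it does not remove the inconsistency. A score that falls in Days 82–96 would also be labelled Day 97 rather than Day 91.

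**Lags of 3–5 days may be uncommon.** For a completer, the schedule puts EOT at Day 91 (+1) after a last dose on Day 90, a lag of 1–2 days. Protocol 8.4.1 spaces the next two visits 7 days apart after EOT, and Table 2 anchors them at last dose +7 and +14. The plan therefore expects EOT close to the last dose. This stands as a point about frequency; the documents give no timing of early EOT visits.

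**A later cut-off brings off-drug scores into treatment-period windows.** SAP 8.4.3 uses +1 day for its last on-treatment ECG value. The Per Protocol Set excludes participants whose Day 91 assessment came 3 or more days after the last dose. Both facts stand. Neither governs the Full Analysis Set, where the estimand takes observed data regardless of discontinuation.

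**A stronger reading to avoid.** A reader might infer that all 356 pairs are lost, or that 13% of early stoppers lose their Day 91 value. The documents do not support either. Visits recorded as scheduled keep their nominal label, which may cover up to 111 of the pairs, and equal weighting of lags and last-dose days has no basis in the plan.

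**Conclusion.** SAP 8.3.2 is internally inconsistent. Read literally, it leaves an early stopper's unscheduled or EOT TETRAS score 2–5 days after the last dose without a window, contrary to its own no-gap statement and to the all-observed-data estimand. On the alternative reading the score is kept but labelled Day 97.

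The number of participants affected is unknown. The direct effect on the primary timepoint is confined to last doses on Days 77–89. For earlier last doses, a lost score bears on Day 91 only indirectly through the MMRM, or not at all where an attended scheduled visit fills the window.

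Three limits apply. Completers' scheduled Day 91 visits are untouched. TETRAS is not scheduled at the early-termination visit, so that visit matters only if the scale happens to be done there. Laboratory and QTcF summaries of potentially clinically significant values at any time do not depend on visit windows. A reader might also infer bias or lost power in the MCP-Mod test, but nothing in the documents allows either to be shown.

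**What to change.** Before database lock, use one cut-off throughout 8.3.2, Table 2 and its note.

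**Preferred:** map unscheduled, EOT and early-termination visits by study day through last dose +5 days, and by days since last dose from +6. Change the note's condition from more than 1 day to at least 6 days. This fits the treatment-policy handling of observed data. The small downside is that scores taken 2–5 days off drug enter treatment-period windows, including Day 91. At lags 3–5 such a Day 91 score would also trigger the Per Protocol exclusion.

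**Alternative:** keep the +1 cut-off and start the Day 97 relative window at last dose +2, changing the note's 6-day wording to match. This keeps off-drug scores out of treatment-period windows. Its cost is that a score taken well before Day 91 is analyzed as Day 97.

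Align the notes to Tables 6 and 7 with whichever is chosen. Check Table 6's last row too: if it is really printed as strictly more than last dose +6 days, an ECG at lag 6 would have no relative window.

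Either option closes the 2–5 day gap. Neither brings TETRAS at lags 11–17 into the analysis, because the Day 104 window excludes it. If scores at lags 2–5 are meant to be left out, say so in 8.3.2 and amend the estimand sentence.

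The cost is a few lines of SAP text, the Table 2 wording and the table notes. It needs no protocol change, visits or data.
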